23.4	URGENT SAFETY MEASURES	
23.5	TEMPORARY HALT	
23.6	Serious Breaches	
23.7	TRIAL REPORTS	
23.8	TRANSPARENCY IN RESEARCH	50
24	EXPENSES AND BENEFITS	50
25	QUALITY ASSURANCE	50
25.1	Risk assessment	
25.2	Monitoring	50
25.3	AUDIT AND REGULATORY INSPECTION	51
26	RECORDS RETENTION & ARCHIVING	
27	PATIENT CONFIDENTIALITY	
28	STUDY FUNDING	
29	SPONSORSHIP AND INDEMNITY	
29.1	Sponsorship	
29.2	INDEMNITY	
29.3	CONTRACTS/AGREEMENTS	52
30	PUBLICATION POLICY	
31	REFERENCES	
APPENDI	IX 1: ECOG PERFORMANCE SCALE	
APPENDI	IX 2: MEASUREMENT OF DISEASE - RECIST CRITERIA	
APPENDI	IX 3: AMENDMENT HISTORY	

PROTOCOL SYNOPSIS

Full Title of study:	A Phase I Trial of the Hypoxia Modifier Atov	-				
Short Title:	Concurrent Chemoradiotherapy in Locally A	-				
Trial Acronym:	Atovaquone with Radical ChemorADIotherapy in locally Advanced NSCLC ARCADIAN					
Clinical Phase:	Phase I					
Study Design:	Single arm, open-label trial utilising Time To Event Continual Reassessment Method					
Study Design.	(TITE-CRM)					
	Objectives	Endpoints				
Primary Endpoint:	To determine the maximum tolerated dose (MTD), and therefore recommended phase II dose (RPTD), of atovaquone when	The dose of atovaquone associated with no more than 48% dose limiting toxicity (DLT) rate (target toxicity level)				
	combined with radical concurrent chemoradiotherapy in patients with non- small cell lung cancer (NSCLC)					
Secondary Endpoints:	To assess the safety and toxicity profile of atovaquone in combination with radical concurrent chemotherapy for NSCLC	Adverse events graded per Common Terminology Criteria for Adverse Events (CTCAE) v4.03				
	To confirm feasibility of measuring hypoxia metagene signature using 3'RNA- Seq in diagnostic NSCLC samples	Hypoxia metagene signature from diagnostic tissue using 3'RNA-Seq				
	To assess agreement of FMISO PET-CT with plasma miR-210 level and tumour hypoxia gene expression pre-treatment with atovaquone	 Tumour hypoxic volume determined by FMISO PET-CT Plasma miR-210 level Hypoxia metagene signature from diagnostic tissue using 3'RNA-Seq 				
	To assess agreement in changes in FMISO PET-CT and plasma miR-210 level following two weeks (+/- 7 days) of atovaquone	 Tumour hypoxic volume determined by FMISO PET-CT Plasma miR-210 level 				
	To assess the tumour response rate at three months (13-15 weeks) following treatment	Response to treatment assessed per Response Evaluation Criteria in Solid Tumours (RECIST) V1.1				
Exploratory Endpoint:	To assess the relationship between plasma atovaquone levels and hypoxia response as measured by FMISO PET-CT and plasma miR-210 level	 Plasma atovaquone concentration Tumour hypoxic volume determined by FMISO PET-CT Plasma miR-210 level 				
Planned enrolment:	20 evaluable participants					
Target Population:	Patients with locally advanced Non-Small Co concurrent chemoradiotherapy					
Investigational Medicinal Products	Name of drug Atovaquone	Formulation, dose, route of administration Suspension, oral, twice daily, dose to be allocated per TiTE-CRM: 450 mg, 600 mg, 675 mg or 750 mg (all doses PO BD)				
	Cisplatin	80 mg/m ² IV on days 1 & 22				
	Vinorelbine	15 mg/m ² IV on days 1, 8, 22 & 29				
Other interventions:						
Study duration:	31 months (start of recruitment to close out)					
Treatment Duration	Up to 9.5 weeks of atovaquone treatment, with concurrent chemoradiotherapy for 6.5 of these weeks					
Follow-up duration	Six months (26-28 weeks) post completion of	of chemoradiotherapy				
End of study	Last Patient Last Visit	· ·				

SUMMARY SCHEDULE OF EVENTS

		ATOVAQUO	NE RUN IN			CHEM	ORADIOTH	ERAPY				FOLLOW UP	
Timing Procedure	Screening ^a	Week -2/-3		Week 1 Day 1 to 7	Week 2	Week 3	Week 4	Week 5	Week 6	Week 7 ^c	Week 10-13 1 month (3-6 wks) post-CRT Day 64 to 91	Week 20-22 3 months (13-15 wks) post-CRT Day 134-154	Week 33-35 6 months (26-28 wks) post-CRT Day 231-245
Informed consent	х	Day -21 to -8	Day -7 10 -1	Day 1 to 7	Day 8 to 14	Day 15 to 21	Day 22 to 28	Day 29 (0 33	Day 30 to 42	Day 45 to 45	Day 04 (0 51	Day 134-134	Day 231-245
Vital signs	х	Xd	Х		Х	Х	Х	Х	Х	Х			
Height	Х												
Weight	Х		Х		Х	Х	Х	Х	Х	Х			
Physical exam	Х	Xd	Х		Х	Х	Х	Х	Х	Х	Х	Х	
ECOG performance status	Х	Xd	Х		Х	Х	Х	Х	Х	Х	Х	Х	
Haematology & biochemistry ^e	Х	Xd	Х		Х	Х	Х	Х	Х	Х			
Pregnancy test (WOCBP only)	Х				Х				Х		Х		
Medical history	Х												
Pulmonary function tests (FEV1 and TLCO)	X ^f												
CT or PET-CT scan ^g	X ^h											Xi	
Atovaquone dispensing		Х		New bottl	e to be disp	ensed as red	quired, each	contains u	p to 21 days	treatment			
Atovaquone treatment completion ^j		XXXXXXX XXXXXXX	XXXXXXX XXXXXXX	XXXXXXX XXXXXXX	XXXXXXX XXXXXXX	XXXXXXX XXXXXXX	XXXXXXX XXXXXXX	XXXXXXX XXXXXXX	XXXXXXX XXXXXXX	XXX XXX			
Radiotherapy	CT simula	tion and RT pl	anning	XXXXX	XXXXX	XXXXX	XXXXX	XXXXX	XXXXX	XXX			
Cisplatin ^k				Х			Х						
Vinorelbine ^l				Х	Х		Х	Х					
Request diagnostic tissue for hypoxia metagene		х											
PK blood sample		Х	Х										
Research blood sample for hypoxia biomarkers ^m		х	Х										
FMISO PET-CT		х	Х										
Atovaquone dosing compliance review			Х	Х	Х	Х	Х	Х	Х	Х			
AE assessment	Х	Х	Х	Х	Х	Х	Х	Х	Х	Х	Х	Х	Х
DLT assessment		Xn	Х	Х	Х	Х	Х	Х	Х	Х	Х	Х	
Concomitant medications	Х	Х	Х	Х	Х	Х	Х	Х	Х	Х	Х	Х	
Commencement of other cancer therapies ⁰												Х	

^a Eligibility tests and patient registration should be completed within two weeks of receiving a screening number (see section 4.5)

^b The end of atovaquone run in appointment (including FMISO PET-CT scan) should be carried out as close to day 1 of CRT as possible (ideally Friday of week -1 with CRT commencing Monday of week 1, but within a maximum of one week prior to commencing CRT)

^c The week 7 visit should ideally be held on the last day of RT

^d Week -2/-3 assessments need not be repeated if screening tests have been carried out within 2 weeks of atovaquone dispensing visit

e Haematology & biochemistry (Haematology - haemoglobin, white blood cells with differential neutrophils and lymphocyte count and platelets; Biochemistry - sodium, potassium, calcium, phosphate, urea, creatinine, total protein, albumin, bilirubin, alkaline phosphatase, aspartate aminotransferase and/or alanine aminotransferase and lactate dehydrogenase; International Normalised Ratio). Tests will be carried out locally in site labs

^f Previously completed standard of care FEV1 & TLCO need not be repeated, provided this is within 90 days of informed consent date

- ^h Previously completed standard of care PET-CT or CT scans need not be repeated provided this is within 60 days of informed consent date
- Patients prescribed Durvalumab may have their follow-up CT scan up to 17 weeks post-CRT (i.e. up to week 24)
- ¹ Atovaquone taken orally, twice daily, at dose selected per process defined in section 17.3

^k Cisplatin (80 mg/m² IV) administered on D1 & 22

¹ Vinorelbine (15 mg/m² IV) administered on D1, 8, 22 & 29

^m miR-210

- ⁿ This visit falls within the DLT reporting period. However, DLTs will be retrospectively reported from the week -1 visit
- ° E.g. Durvalumab, if clinically indicated

^g CT or PET-CT of brain/chest/abdomen or chest/abdomen/pelvis, as per local standard of care

STUDY SCHEMA

ABBREVIATIONS

¹⁸F-fluoromisonidazole **FMISO** 3'RNA-seq 3' RNA-sequencing ADR Adverse drug reaction AE Adverse Event ALT Alanine aminotransferase ANC Absolute neutrophil count AP/PA Anterior posterior/posterior anterior AST Aspartate aminotransferase ATOM Atovaquone as Tumour HypOxia Modifier ΒD Twice daily ΒP **Blood** pressure BSA Body surface area С Celsius CAIX Carbonic Anhydrase IX (9) CBCT Cone Beam Computed Tomography Centimetre cm CR Complete response CRF **Case Report Form** CRT Chemoradiotherapy СТ **Computed Tomography** CTA **Clinical Trials Authorisation** CTA **Clinical Trials Agreement** CTCAE Common Terminology Criteria for Adverse Events CTV Clinical target volume DAHANCA Danish Head and Neck Cancer Group DLT Dose limiting toxicity $\mathsf{D}_{\mathsf{max}}$ Maximum dose DRR Digitally reconstructed radiograph EBUS Endobronchial ultrasound ECG Electrocardiogram ECOG Eastern Cooperative Oncology Group eCRF **Electronic Case Report Form** ELISA Enzyme-linked immunosorbent assay EU **European Union** Forced expiration volume FEV1 FFPE Formalin-fixed paraffin-embedded Gramme g GCP **Good Clinical Practice** General Data Protection Regulation GDPR GP General practitioner GSK GlaxoSmithKline GTV Gross tumour volume Gy Gray (radiation dose unit) Hb Haemoglobin Human chorionic gonadotropin HCG HIV Human immunodeficiency virus HPLC High Performance Liquid Chromatography HRA Health Research Authority HTA Human Tissue Act ΗV Hypoxic volume IB Investigator brochure ICRU International Commission on Radiation Units and Measurements IGRT Image-guided radiation therapy IMP **Investigational Medicinal Product** IMRT Intensity modulated radiotherapy International normalised ratio (blood clotting test) INR

ISF	Investigator site file
ITV	Internal target volume
IUD	Intrauterine device
IV	Intravenous
kV-CBCT	Kilo-voltage cone beam computed tomography
L	Litre
LDH	Lactate dehydrogenase
LPLV	Last visit of the last patient undergoing the trial
m	Metre
MBq	Megabecquerel (unit of radioactivity)
mg	Milligrammes
MHRA	Medicines and Healthcare Products Regulatory Authority
miR-210 mL	A MicroRNA with altered expression in tumour tissue Millilitre
MLC	Multileaf collimator
mm	Millimetre
MRC	Medical Research Council
MRI	Magnetic Resonance Imaging
MTD	Maximum tolerated dose
MV	Megavoltage
NCCN	National Comprehensive Cancer Network
NCI	National Cancer Institute
NE	Not evaluated
NHS	National Health Service
NIHR	National Institute of Health Research
nIMP	Non-Investigational Medicinal Product
NSCLC	Non-small cell lung cancer
OAR	Organs at risk
OCR	Oxygen consumption rate
ОСТО	Oncology Clinical Trials Office
OCTRU	Oxford Clinical Trials Research Unit
OPD	Outpatient Department
РСР	Pneumocystis pneumonia
PD	Pharmacodynamics
PD	Progressive disease
PDPP	Protocol decision point plan
PET	Positron Emission Tomography
pg	Picogrammes
PI	Principal Investigator
РК	Pharmacokinetics
PO	Administered orally
PPI	Proton pump inhibitor
PR	Partial response
PRV	Positioning reference volume
PTV	Planning target volume
QA	Quality assurance
qRT-PCR	Quantitative reverse transcription polymerase chain reaction
R&D	Research and development
RA REC	RapidArc Research Ethics Committee
RECIST	
RIOC	Response evaluation criteria in solid tumours Radiotherapy & Imaging Oversight Committee
RPTD	Recommended Phase Two Dose
RSI	Reference Safety Information
RT	Radiotherapy
RT/LT	Right/left
RTOG	Radiation Therapy Oncology Group
RTP	Radiation treatment planning
RTTQA	Radiotherapy trials quality assurance
	nadiotherapy that quality assurance

SAE	Serious Adverse Event
SAR	Serious Adverse Reaction
SD	Stable disease
SDV	Source data verification
SmPC	Summary of Product Characteristics
SOC	Standard of care
SOP	Standard operating procedure
SUP/INF	Superior/inferior
SUSAR	Suspected Unexpected Serious Adverse Reaction
SUV	Standardised uptake value
TBR	Tumour to blood ratio
TD5/5	Tolerance dose yielding 5% risk of a particular outcome at 5 years
TDS	Three times daily
TITE-CRM	Time To Event Continual Reassessment Method
TLCO	Transfer factor of the lung for carbon monoxide
TMG	Trial Management Group
μmol	Micromoles
Vx	Lung volume receiving $\geq X$ Gy of radiation
VEGF	Vascular Endothelial Growth Factor
VMAT	Volumetric modulated arc therapy
WBC	White blood cell(s)
WOCBP	Women of child bearing potential

1 INTRODUCTION

1.1 Background

Patient population

Lung cancer is the leading cause of cancer death in the UK with non-small cell lung cancer (NSCLC) accounting for approximately 85% of cases [1]. A third of patients with NSCLC present with locally advanced (stage III) non-metastatic disease and treatment with concurrent chemoradiotherapy has become the standard of care for patients with good performance status. However, despite significant improvements in technical radiotherapy delivery, clinical outcomes for patients treated with 'curative intent' remain extremely poor with survival rates at five years largely unchanged at only 15% [2]. Suboptimal locoregional control contributes to these poor outcomes and therefore developing novel radiosensitisers for this purpose represents a significant unmet clinical need for this patient population.

Tumour hypoxia and radiotherapy

Many solid tumours, including NSCLC, are typically dependent upon an abnormal, poorly functioning vasculature for oxygen delivery [3]. Coupled with the high metabolic requirements of many tumours, this leads to an imbalance in oxygen supply and demand. The resulting hypoxic microenvironment is recognised as promoting an aggressive phenotype, including resistance to drug treatment, and increased metastatic potential [4]. Although tumour hypoxia is associated with adverse patient outcomes regardless of which treatment modality is used, the profound radiation resistance caused by tumour hypoxia leads to particularly poor outcomes for patients treated with radiotherapy or CRT [5]. There is therefore significant interest in developing effective hypoxia modifying therapies which can be safely combined with radiotherapy.

Previous hypoxia modifying strategies aimed at overcoming hypoxia-induced radioresistance have primarily focused on improving the oxygen supply to tumours. These have unfortunately yielded only limited success and none are currently in widespread routine clinical use. The reasons for this are multifactorial and include poor trial design, absence of predictive therapeutic biomarkers and the use of sub-optimal hypoxia modifying agents [6]. In particular, the importance of appropriately selecting patients who will benefit from hypoxia targeted therapy has become well-recognised. For example, it has been demonstrated retrospectively that the addition of nimorazole, an oxygen mimetic, to radiotherapy treatment in patients with head and neck cancer (DAHANCA 5) would have resulted in significantly greater clinical benefits (locoregional control and disease specific survival) if a hypoxia gene expression classifier had been used to select patients with hypoxic tumours [7]. In a separate study in this tumour site, patients with tumours classified as hypoxic using ¹⁸F-fluoromisonidazole (FMISO) PET-CT imaging had greater benefit from the addition of the hypoxia-activated cytotoxic agent tirapazamine when combined with chemoradiotherapy [8].

Therefore, a paradigm shift in the approach to addressing tumour hypoxia in clinical studies is required to prevent further futile trials in this field, with the focus not only on developing deliverable and more efficacious agents, but also on using hypoxia biomarkers to enable appropriate patient selection for treatment.

This study will be the first trial to combine atovaquone, a promising novel hypoxia modifier with radiation and aims to assess safety whilst developing candidate hypoxia biomarkers to further confirm efficacy and guide future hypoxia trial design.

1.2 Investigational Medicinal Products used in the study

Atovaquone

Atovaquone has EU marketing authorisation and is indicated for acute treatment of mild to moderate Pneumocystis pneumonia (PCP). It is also used in combination with proguanil for malaria prophylaxis. The recommended oral (PO) dose for PCP is 750 mg (5 mL) twice a day (BD) for 21 days.

In vitro studies have demonstrated that atovaquone at clinically relevant concentrations significantly reduces oxygen consumption in a number of tumour cell lines [9]. Subcutaneous murine tumour models have been used to confirm that oral atovaquone causes a significant reduction in tumour hypoxia. Our data suggests that atovaquone causes these effects by reducing oxidative phosphorylation in mitochondria.

750 mg BD oral atovaquone has also been demonstrated to reduce tumour hypoxia in patients with NSCLC in the ATOM (Atovaquone as Tumour HypOxia Modifier) window-of-opportunity study (unpublished data). ATOM participants received 7-17 days treatment with atovaquone, shorter than the treatment duration for PCP, but sufficient for blood atovaquone levels to reach steady state.

Atovaquone was exceptionally well tolerated by ATOM participants with very few side effects reported. The ATOM trial protocol included an option to escalate atovaquone dose to 1000 mg BD if no effect on tumour hypoxia was seen at 750 mg BD, however efficacy was seen at 750 mg and therefore the higher dose was not investigated. Higher dosing regimens [750 mg three times daily (n=8) and 1500 mg twice daily (n=8)] have been given safely in HIV infected volunteers [10].

Participants in the ATOM trial were awaiting surgery for NSCLC and received no concurrent chemotherapy or radiotherapy. In recognition that ARCADIAN will combine atovaquone with concurrent chemoradiotherapy (CRT), the first participants will receive a lower dose of atovaquone (450 mg BD). Pre-clinical data gives no indication that atovaquone will exacerbate the side effects of CRT, but such an effect cannot be conclusively ruled out. Escalation to doses of atovaquone up to and including 750 mg BD, if appropriate, will be guided by the Time-to-Event Continual Reassessment Method (TiTE-CRM) statistical model.

ARCADIAN participants will receive two weeks (+/- 7 days) of treatment with atovaquone prior to commencing CRT. As demonstrated in the ATOM trial, seven days of treatment is sufficient to achieve a reduction in tumour hypoxia. Patients will not have their CRT delayed due to enrolment on the trial, as atovaquone run in will occur while patients are waiting for their standard of care CRT to begin. Atovaquone treatment will then continue concurrently with CRT, for a total duration of 59 days (+/- 7 days).

Cisplatin and vinorelbine

Concurrent CRT is the standard of care for patients with locally advanced NSCLC and good performance status. The CRT regime used is variable across the UK with variation in the type of chemotherapy (e.g. cisplatin and etoposide vs. cisplatin and vinorelbine) and the number of cycles of chemotherapy (two or four). Participants in the ARCADIAN trial will receive two cycles of cisplatin and vinorelbine. This has been selected due to being a widely accepted regimen in the UK, and one that is deliverable at the intended research sites. Vinorelbine has also been chosen in preference to etoposide as atovaquone has been found to increase plasma levels of etoposide and its metabolite when given for PCP prophylaxis to children undergoing treatment for acute lymphoblastic leukaemia.

1.3 Other research interventions

Radiotherapy

Concurrent CRT is the standard of care for patients with locally advanced NSCLC and good performance status. There is variation in the radiotherapy regime used across the UK, with schedules delivered as standard of care including 55 Gy in 2.75 Gy fractions, 60 Gy in 2 Gy fractions and 66 Gy in 2 Gy fractions. Participants in the ARCADIAN trial will receive 66 Gy in 33 fractions of 2 Gy. This is an established treatment regimen in the UK and deliverable at the intended research sites.

FMISO PET-CT

The most widely used method for measuring tumour hypoxia in the clinical setting is PET imaging with radiotracers which accumulate in hypoxic tissues, such as ¹⁸F-misonidazole (FMISO). This particular method has been shown to be more effective at detecting reoxygenation states than alternative techniques [11]. The imaging and reconstruction protocols on the scanners at Oxford and Edinburgh will be set up by the collaborating physicist to ensure high quality and comparable FMISO PET-CT data from both sites is obtained. Scan analysis will be conducted by a PET-CT consultant radiologist and physicist in Oxford with extensive experience in FMISO PET-CT using well-recognised tumour-to-blood parameters. In the event that FMISO is unavailable (e.g. due to failure in the manufacturing process), trial participants will continue in the study, but will not be required to undergo tumour hypoxia imaging.

FMISO PET-CT technique:

An activity of 370 MBq (+/- 10%) of FMISO will be injected and a 10-minute acquisition image obtained four hours postinjection. CT will be performed for localisation and PET attenuation correction (a 4DCT technique will be used where possible). Tumour outlining will be performed by an experienced PET-CT radiologist and any metastases (nodal or extranodal) identified within the PET field of view also outlined and included in the analysis. A background mean standardised uptake value (SUV_{mean}) should be obtained by outlining blood in the descending aorta. To determine the tumour hypoxic volume (HV), voxel-by-voxel SUVs will be divided by the background SUV_{mean} to provide tumour-toblood ratio (TBR) values for each tumour voxel. Voxels with TBR \ge 1.4 will be classified as hypoxic, consistent with previously published data [12]. Volumes of hypoxic voxels before and after atovaquone treatment will be compared and a \ge 10% reduction in hypoxic volume (HV) will be defined as a response. HV measurements will also be compared to plasma hypoxia marker data and hypoxia metagene signature data. Additional information can be found in the separate imaging guidelines document.

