3 OBJECTIVES AND ENDPOINTS

Primary Objective	Endpoints/ Outcome measures	Time point(s) of evaluation of this end point
 To determine the maximum tolerated dose (MTD), and therefore recommended phase II dose (RPTD), of atovaquone when combined with radical concurrent chemoradiotherapy in patients with non-small cell lung cancer (NSCLC) 	 The dose of atovaquone associated with no more than 48% dose limiting toxicity (DLT) rate (target toxicity level) 	• From week -2/-3 until three months post-completion of CRT
Secondary Objectives		
 To assess the safety and toxicity profile of atovaquone in combination with radical concurrent chemotherapy for NSCLC 	 Adverse events graded per Common Terminology Criteria for Adverse Events (CTCAE) v4.03 	 From screening/baseline until six months post completion of CRT
 To confirm feasibility of measuring hypoxia metagene signature using 3'RNA-Seq in diagnostic NSCLC samples 	 Hypoxia metagene signature from diagnostic tissue using 3'RNA-Seq 	At baseline
 To assess agreement of FMISO PET-CT with plasma miR-210 level and tumour hypoxia gene expression pre-treatment with atovaquone 	 Tumour hypoxic volume determined by FMISO PET-CT Plasma miR-210 level Hypoxia metagene signature from diagnostic tissue using 3'RNA-Seq 	 Week -2/-3 (prior to atovaquone treatment)
 To assess agreement in changes in FMISO PET-CT and plasma miR- 210 level following two weeks (+/- 7 days) of atovaquone 	 Tumour hypoxic volume determined by FMISO PET-CT Plasma miR-210 level 	 Week -2/-3 (prior to atovaquone treatment) Following two weeks (+/- 7 days) of atovaquone treatment
 To assess the tumour response rate at three months following treatment 	 Response to treatment assessed per Response Evaluation Criteria in Solid Tumours (RECIST) V1.1 	Three months post completion of CRT
Exploratory Objectives		
To assess the relationship between plasma atovaquone levels and hypoxia response as measured by FMISO PET- CT and plasma miR-210 level	 Plasma atovaquone concentration Tumour hypoxic volume determined by FMISO PET-CT Plasma miR-210 level 	 Week -2/-3 (prior to atovaquone treatment) Following two weeks (+/- 7 days) of atovaquone treatment

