4.1 Eligibility criteria for entry into the study

Inclusion criteria:

A patient will be eligible for inclusion in this study if all of the following criteria apply:

- 1. Histologically or cytologically confirmed diagnosis of locally advanced NSCLC and selected for treatment with full dose radical concurrent CRT
- 2. At least one measurable lesion greater than 2 cm maximal length in any direction on routine imaging (CT or PET-CT scan performed in the 60 days prior to consent)
- 3. Male or female, age \geq 18 years
- 4. ECOG performance status 0 or 1
- 5. Adequate pulmonary function tests for thoracic radiotherapy (FEV1 and TLCO, >40% predicted)
- 6. Haematological and biochemical indices within the ranges shown below:

Lab Test	Value required
Bilirubin	≤1.5 x upper limit of normal (ULN)
ALT and/or AST	≤2.5 x ULN
Creatinine clearance	Calculated creatinine clearance (using
	Cockcroft-Gault or Wright formula) or
	measured* creatinine clearance ≥60 mL/min
Absolute neutrophil count	≥1.5x10 ⁹ /L
Platelets	≥100x10 ⁹ /L
Haemoglobin	≥90 g/L
INR	≤1.5

* The radioisotope method of assessing glomerular filtration rate may be utilised if clinically indicated

- 7. The patient is willing and able to comply with the protocol scheduled follow-up visits and examinations for the duration of the study
- 8. Written (signed and dated) informed consent and be capable of co-operating with protocol

4.2 Exclusion criteria:

A patient will not be eligible for the trial if any of the following apply:

- 1. Pregnant or breast-feeding women, or women of childbearing potential unless effective methods of contraception are used
- 2. Previous systemic chemotherapy or biological therapy within 21 days of commencing atovaquone treatment
- 3. Treatment with any other investigational agent as part of a clinical trial within 28 days of study enrolment
- 4. Previous thoracic radiotherapy
- 5. Known previous adverse reaction to atovaquone or its excipients
- 6. Active hepatitis, gallbladder disease or pancreatitis
- 7. Impaired gastrointestinal function that may significantly alter absorption of atovaquone
- 8. Concurrent administration of warfarin in the 14 days prior to starting atovaquone
- 9. Concurrent administration of known electron transport chain inhibitors (e.g. metformin). A wash-out period prior to administration of atovaquone is required (e.g. 4 days for metformin). Refer to section 10.3 for further details.

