7.2.3 Hypoxia metagene expression

In cases with sufficient diagnostic tissue, a section of formalin-fixed paraffin-embedded (FFPE) tissue will be obtained and sent to a central laboratory for tumour tissue extraction and hypoxia metagene analysis using the 3'RNA-seq method. This is the optimal technique available to obtain such data from limited and low quality FFPE tissue samples, as is often the case in NSCLC.

More specifically, a previously validated hypoxia gene expression signature will be measured using diagnostic biopsy FFPE samples. We will utilise 3'RNA-seq as it has clear advantages over alternative and now more dated sequencing and array techniques. 3'RNA-seq can accurately estimate gene expression even if applied to low quality or degraded samples and it requires only 100 pg total RNA input. This is an important consideration in our patient population, as diagnostic tissue can often be very scarce. Importantly, modern RNA-seq techniques are relatively inexpensive and when performed on already obtained diagnostic tissue can be easily incorporated into larger clinical studies, or potentially routine diagnostic work-up thereafter.

We will not require patients to undergo additional tissue sampling in appreciation of the difficulty and often repeated attempts required to obtain sufficient diagnostic tissue in this patient population. Also, given the short time window to get patients on treatment and to start CRT, mandating additional tissue may result in a delay in treatment that we feel would be unacceptable.

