6. ANALYSIS

6.1 Outcome Definitions

Primary outcome

To determine the maximum tolerated dose (MTD), and therefore recommended phase II dose (RPTD), of atovaquone when combined with radical concurrent chemoradiotherapy

The outcome is the occurrence (yes/no) of a DLT within the DLT assessment period. For patients without a DLT, time observed within the DLT assessment period will also be taken into account in the analysis. The total i.e. maximum duration of the DLT assessment period for each patient is the length of the atovaquone run-in period (1-3 weeks) which will be pre-specified before the patient starts treatment, plus the length of CRT treatment (6.5 weeks= 45 days) plus follow-up duration (12 weeks = 84 days). At final analysis, patients without a DLT will have completed the DLT period unless they withdrew early. The MTD will be the dose level with posterior mean DLT rate closest to the target toxicity level of 48% when the dose-toxicity model is updated for the final analysis.

For the definition of a DLT, see Appendix 4.

Secondary outcomes

To assess the safety and toxicity profile of atovaquone in combination with radical concurrent chemotherapy

Adverse events from the first dose of atovaquone to six months post completion of CRT will be presented (see Appendix 3).

To confirm feasibility of measuring hypoxia metagene signature using 3'RNA-Seq in diagnostic NSCLC samples

To assess agreement of FMISO PET-CT with plasma miR-210 level and tumour hypoxia gene expression pretreatment with atovaquone

Hypoxia assessed using the baseline FMISO PET-CT scan will be measured using tumour to blood ratio (TBRvolume) (ml).

Plasma miR-210 level will be derived from the baseline blood sample.

Baseline is at week -2/-3 prior to receiving the first dose of atovaquone.

To assess agreement in changes in FMISO PET-CT and plasma miR-210 level following two weeks (+/- 7 days) of atovaquone

Change in FMISO PET-CT will be the % change between TBRvolume (ml) derived from the baseline and pre-CRT scans.

Change in plasma miR-210 level will be the % change between miR-210 level derived from the baseline and pre-CRT blood samples.

Baseline is at week -2/-3 prior to receiving the first dose of atovaquone and pre-CRT is at week -1 (two weeks (+/- 7 days) after starting atovaquone and prior to receiving any CRT.

To assess the tumour response rate at three months following treatment

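### Absolute hypoxic volume depends on tumour size, so used alone it can understate baseline agreement between FMISO PET-CT and the metagene

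*Protocol*

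**What the plan says.** One secondary objective in protocol section 3 is: "To assess agreement of FMISO PET-CT with plasma miR-210 level and tumour hypoxia gene expression pre-treatment with atovaquone". The FMISO endpoint listed for it is tumour hypoxic volume, and no other FMISO measure is listed.

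Protocol section 1.3 describes how that volume is obtained. The tumour is outlined, with "any metastases (nodal or extranodal) identified within the PET field of view also outlined and included in the analysis". Each voxel's uptake is divided by the blood background to give a tumour-to-blood ratio (TBR). Voxels with a TBR of at least 1.4 "will be classified as hypoxic, consistent with previously published data", and hypoxic volume is the volume of those voxels. The section then says: "HV measurements will also be compared to plasma hypoxia marker data and hypoxia metagene signature data".

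The metagene comes from existing diagnostic material. Section 7.2.3 says that "a section of formalin-fixed paraffin-embedded (FFPE) tissue will be obtained and sent to a central laboratory" where tissue suffices, and adds: "We will not require patients to undergo additional tissue sampling".

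Entry (section 4.1) requires "At least one measurable lesion greater than 2 cm maximal length in any direction on routine imaging" and sets no upper limit on size.

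SAP 6.1 gives the scale of the baseline scan measure: "Hypoxia assessed using the baseline FMISO PET-CT scan will be measured using tumour to blood ratio (TBRvolume) (ml", that is, an absolute volume in millilitres. SAP 2.2 prints an analysis population for FMISO against miR-210 but none for FMISO against gene expression, and says that objectives shaded grey fall outside the SAP. SAP 6.2 plans no formal analysis of the secondary objectives.

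**The concern.** The two quantities answer different questions. The metagene score describes how hypoxic the sampled tissue is; a larger lesion, or more lesions, does not by itself raise it. Hypoxic volume rises with the amount of disease even when the degree of hypoxia is unchanged. Neither document divides hypoxic volume by outlined volume, adjusts for tumour size, ties the scan measure to the sampled lesion, or provides for recording the biopsy site for that purpose.

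The comparison has a stated use. Section 1.4 of the protocol wants alternatives to FMISO because FMISO is impractical in large trials, and intends the results to shape a strategy for selecting patients with hypoxic tumours. If spread in tumour size masks the relationship, a useful tissue marker may look weaker than it is. The data set is small: 20 evaluable patients, and fewer with both measures, because tissue is sent only where there is enough and patients continue without the scan if FMISO is unavailable.

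**Working it through.** The documents give no agreement statistic, target or sample size for this comparison, so there is no planned figure to reproduce. Spreads of tumour size and hypoxic fraction are not given either; those below are assumptions.

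**Step 1: size effect at fixed hypoxia.** Treat a lesion of diameter d as a sphere, with volume π/6 × d³, and assume a hypoxic fraction of 20%.

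- d = 2 cm (the entry limit): volume 4.2 mL, hypoxic volume 0.84 mL.
- d = 6 cm: volume 113.1 mL, hypoxic volume 22.6 mL.
- Ratio: (6/2)³ = 27, with the same degree of hypoxia in both.

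**Step 2: ceiling for a perfect score.** Write log HV = log V + log f, where HV is hypoxic volume, V outlined volume and f hypoxic fraction. Let sv and sf be the SDs of log V and log f. If V and f are independent, a score that measures f perfectly correlates with log HV at sf / √(sf² + sv²).

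- sf = 0.6, sv = 1.0: 0.6 / √(0.36 + 1.00) = 0.51.
- sf = 0.4, sv = 1.3: 0.4 / √(0.16 + 1.69) = 0.29.
- sf = 0.8, sv = 0.7: 0.8 / √(0.64 + 0.49) = 0.75.

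**Step 3: independence relaxed.** Let c be the correlation of log V with log f, and ρ the correlation of the score with log f. If the score is linked to V only through f, then

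corr(score, log HV) = ρ × (sf + c·sv) / √(sv² + sf² + 2c·sv·sf).

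The grid takes diameters from 2 cm up to 4–10 cm, fractions from 10–40% to 2–80%, and c = 0, 0.3 and 0.6. Each range is read as ±2 SD on the log scale, so sv = 3·ln(d_max/2)/4 and sf = ln(f_max/f_min)/4. With ρ = 0.7:

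| Setting | sv | sf | c = 0 | c = 0.3 | c = 0.6 |
|---|---|---|---|---|---|
| 2–10 cm, 10–40% | 1.21 | 0.35 | 0.19 | 0.37 | 0.52 |
| 2–8 cm, 5–50% (middle case) | 1.04 | 0.58 | 0.34 | 0.47 | 0.58 |
| 2–4 cm, 2–80% | 0.52 | 0.92 | 0.61 | 0.64 | 0.66 |

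The first and last rows contain the extremes of the full grid, 0.19 and 0.66. The correlation falls in every setting. Log V explains between 24% and 96% of the variance of log HV (middle case 77–90%).

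**Step 4: visibility at this sample size.** Simulated Spearman correlations (1500 repetitions per setting, four of the spread settings, ρ = 0.7) give the chance of a positive result at p < 0.05. That threshold is only a yardstick, since SAP 4.1 sets no significance level.

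- n = 20: 91–93% with hypoxic fraction, 12–84% with hypoxic volume (middle case 27%, 51% and 73% for c = 0, 0.3 and 0.6).
- n = 15: 79–83% with fraction, 9–70% with volume.

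These steps do not model biopsy sampling error or differences between lesions, which would weaken the observed agreement on either measure.

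**The case against.** The strongest case on the other side has five parts.

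- **The SAP sentence may not govern this comparison.** Under the agreement objective, SAP 6.1 defines only the scan volume and miR-210, and SAP 2.2 prints no population for the metagene comparison. The grey shading is lost in the text, but that objective probably lies outside the SAP. This stands, so the point rests on protocol 1.3 and section 3.
- **Unseen documents may cover it.** The imaging guidelines and the SAP appendix of tables and figures are separate. The claim is therefore confined to the protocol and SAP as supplied.
- **Summing and a single lesion are not stated.** A reader might infer that one biopsied lesion is set against a total over all disease. One volume per patient and one tissue section make that natural, but the protocol says only that metastases are included in the analysis, and it does not say where the tissue was taken.
- **Dominance by size is not shown.** A reader might infer that tumour size drives the comparison. The documents give no spreads, and if larger tumours are also proportionally more hypoxic the loss is modest: 0.58 against 0.70 in the middle case at c = 0.6.
- **No rule would discard the marker.** A reader might infer that the trial could reject the metagene wrongly. There is no threshold or go/no-go rule, and the results are descriptive.

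None of this removes the mismatch. A scatterplot of hypoxic volume against the score shows the same weakening as a coefficient would. Hypoxic volume was used in the earlier ATOM trial (protocol 1.4) to measure change within patients, where baseline size largely cancels; that does not carry over to a comparison between patients.

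**Conclusion.** The point holds for the baseline FMISO–metagene comparison only. As the supplied documents stand, a measure that depends on tumour size is set beside a score with no direct dependence on size, without normalisation or lesion matching, and the comparison can understate real agreement. The likely harm is a misleading descriptive result.

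The direction follows from the definition of hypoxic volume, provided that the score relates to volume only through hypoxic fraction. The size cannot be settled from the documents. Under the assumed spreads, a true correlation of 0.7 becomes 0.19 to 0.66, which runs from a severe loss to a slight one. The percent-change endpoint is largely unaffected, and total hypoxic volume may be a reasonable comparator for plasma miR-210. This is an inexpensive improvement to a secondary objective and has no bearing on dose finding.

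**What to change.** In protocol 1.3 and section 3, and in whichever analysis document covers the metagene objective:

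- Keep hypoxic volume as the stated endpoint.
- Prespecify reporting beside it the hypoxic fraction, defined as the volume with TBR of at least 1.4 divided by the outlined volume. Give it for the biopsied lesion where that lesion can be matched, and otherwise for all outlined disease, stating which applies to each patient.
- Report total outlined volume.
- Record biopsy site and date.

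Leave the miR-210 comparison and the percent-change endpoint as planned.

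Lesions are already outlined and classified voxel by voxel, so no extra scan or tissue is needed. The cost is a little added analysis and lesion-matching work, two recorded items, and some patients reported as unmatched. Making the biopsied-lesion fraction the main measure instead would lose those patients from an already small set, which is why it is proposed as an addition.
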